### 7.5.2 Analysis of Secondary Efficacy Endpoints

Full analysis set will be used for all secondary efficacy analyses. The proportion of subjects with TG <500 mg/dL at Week 8 will be summarized by treatment group and analyzed using Cochran Mantel Haenszel (CMH) method stratified by the 2 stratification. Unstratified Chi-square test will be performed for comparisons between the placebo and the individual dose group or if the sample size within a stratum is too small (< 5 subjects). In addition, responder analysis at Week 8 will be performed to ensure the consistency of the results. The following threshold will be used to calculate: the proportion of subjects with TG normalized; with TG reduction by  $\geq 30\%$ ,  $\geq 40\%$ ,  $\geq 50\%$ ,  $\geq 60\%$ ,  $\geq 70\%$ ,  $\geq 80\%$ , and  $\geq 90\%$  from baseline.

Cumulative distribution function of both percentage changes from baseline and changes from baseline for TG at Week 8 by treatment group will be summarized descriptively and graphically.

Percentage change in VLDL-C, LDL-C, non-HDL-C, HDL-C, VLDL-TG, ApoB, hsCRP, fasting plasma glucose, adiponectin, and body weight from baseline to Week 8 will be analyzed similarly as the primary endpoints. For parameters that only have one post-baseline measurement, an ANCOVA model will be performed with treatment and background therapy as factors and baseline value as covariate.

## 7.6 SAFETY ANALYSIS

All safety analyses will be performed using the Safety Analysis Set. Safety data presented by treatment group will be summarized on an 'as treated' basis. Safety variables include treatment-emergent adverse events (TEAEs), concomitant medication use, physical examination, clinical laboratory parameters, vital signs, and ECG results. [REDACTED] for all safety analyses is defined as the date of the first dose of investigational product.

### 7.6.1 Adverse Events

Subject incidence of TEAEs will be tabulated by Medical Dictionary for Regulatory Activities (MedDRA, Version 23.0) system organ class, MedDRA preferred term, and

treatment groups. All TEAEs, all treatment-emergent related AEs, all TESAEs, and all treatment-emergent serious related AEs, the most severe CTCAE grade, TEAEs leading to IP discontinuation, and TESAEs leading to IP discontinuation will be summarized. Related is defined as “possibly related”, “probably related”, or “definitely related” to randomized investigational medicinal product. Subjects will be counted only once within a SOC and Preferred Term (PT), even if the subject experienced more than one TEAE within a specific SOC and PT, and PT only.

All AEs, TESAEs, TEAEs leading to IP discontinuation, Fatal TEAEs and COVID-19 related AEs will be listed.

### 7.6.2 Clinical Laboratory Parameters

The following laboratory assessments will be analyzed using the safety analysis set:

**Hematology:** White Blood Cell (WBC) with differential (Total Neutrophils, Lymphocytes, Monocytes, Eosinophils, Basophils – absolute and %), Red blood cell (RBC) count, RBC Indices (Mean Corpuscular Volume [MCV], Mean Corpuscular Hemoglobin Concentration [MCH], Mean Corpuscular Hemoglobin Concentration [MCHC], Red Cell Distribution Width [RDW], Reticulocyte count) Hemoglobin, Hematocrit, Platelet count, Coagulation panel (including Prothrombin Time, International Normalized Ratio (INR), Activated Partial Thromboplastin Time [aPTT])

**Lipid Assessment:** [REDACTED], ApoB, [REDACTED] non-HDL-C, LDL-C, [REDACTED]  
[REDACTED], TG, VLDL-C, VLDL-TG.

**Clinical Chemistries:** Alkaline Phosphatase (ALP), ALT, AST, Albumin, Bicarbonate, BUN (Blood urea nitrogen), Calcium, Creatinine, eGFR, Creatine Kinase (CK), Chloride, Fasting plasma glucose, Gamma-Glutamyl Transferase (GGT), Lactate dehydrogenase, Magnesium, Phosphorus, Potassium, Sodium, (Total bilirubin, Indirect/direct bilirubin), Total protein, Uric acid. For ALT, change and percent change from baseline at week 8 will be analyzed using MMRM method based on full analysis set.

**Urinalysis:** Basic urinalysis (dipstick, including macroscopic appearance, bilirubin, blood, color, glucose, ketones, leukocyte esterase, nitrite, pH, protein, specific gravity, urobilinogen); Full urinalysis (dipstick plus microscopic evaluation) to be performed only at the screening and End of Study visits). A reflex microscopic urinalysis should be performed if the results of the urinalysis is abnormal or at the discretion of the Principal Investigator (PI) or delegate. A listing will be presented for Urinalysis results.

### Other Study-Specific Laboratory Assessments:

- BIO89-100 level (to be evaluated by bioanalytical laboratory)
- TSH level
- Serum hCG pregnancy test, Urine hCG pregnancy test, FSH level

- Urine drug screen including amphetamines, barbiturates, cocaine metabolites, opiates, benzodiazepines, cannabinoids and phencyclidine
- Virology - Human Immunodeficiency Virus (HIV) antibody, hepatitis B surface antigen (HBsAg, and HCV antibody). To determine current infection status, if HBsAg positive Hepatitis B Virus (HBV) DNA will be measured or if HCV antibody positive, HCV Ribonucleic Acid (RNA) will be measured.
- 24-hour urine for cortisol, [REDACTED], [REDACTED], [REDACTED], total Insulin, hsCRP, [REDACTED], [REDACTED], Serum adiponectin, and [REDACTED]  
[REDACTED].

For all other assessments that are below the lower limit of quantification will be imputed to half of the LLOQ for summarization; assessments that are above the upper limit of quantification will be imputed to the ULOQ for summarization. For listings, records that are LLOQ or ULOQ will be listed as such together with the imputed value in separate columns.

Laboratory results will be presented as received from the central laboratory (or kit provided by the central lab).

Descriptive summaries by treatment groups will be produced for the laboratory tests.

Shifts (low/normal/high) from the relevant baseline tables based on the normal ranges will be constructed. The shifts will be performed from the baseline to each post-baseline visit, and to minimum and maximum post-baseline visit.

### 7.6.3 Vital Signs

The observed values and the change from baseline for vital signs (body temperature, pulse rate, RR, and supine BP) will be summarized by visit and treatment group.

The number and percent of subjects meeting the following criteria will be summarized considering all post-baseline visits including unscheduled:

- Absolute value of SBP < 90 mm Hg
- Absolute value of DBP < 50 mm Hg
- Pulse rate < 50 bpm
- Pulse rate > 120 bpm
- Maximum increase from baseline in SBP  $\geq$  30 mm Hg
- Maximum increase from baseline in DBP  $\geq$  20 mm Hg
- Maximum decrease from baseline in SBP  $\geq$  30 mm Hg

- Maximum decrease from baseline in DBP  $\geq 20$  mm Hg

Clinically significant shifts for blood pressure from baseline to each post baseline visit will be summarized in the following criteria:

**Table 7. Blood Pressure Category**

Systolic (mm Hg)		Diastolic (mm Hg)	Blood Pressure Category
>180	Or	>120	Crisis
$\geq 140$	Or	$\geq 90$	Hypertension Stage 2
130-139	Or	80-89	Hypertension Stage 1
120-129	And	<80	Elevated
<90	Or	<60	Hypotension
<120	And	<80	Normal

Clinically significant shifts for pulse rate from baseline to each post baseline visit will be summarized using the category as <50 bpm; 50-99 bpm,  $\geq 100$  bpm

#### 7.6.4 Physical Examinations

Physical examination (abdominal, cardiovascular, neurological, respiratory, skin, and general, etc) results will be summarized by visits and by treatment group.

Shift tables from baseline to end of the study will be summarized using the category as normal, abnormal but not clinically significant, and abnormal and clinically significant.

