| Physical examination  | X   | x c                                | x c             | x c | x c                   | x c | x c | $x^c$ | x c | x c | x c | X | X                      |
| Body weight   | x   | X   | X                          | X              |                                  |                |                | Х     |                |                |                | x | X                      |
| Height d   | х   |   |                            |                |                                  |                |                |       |                |                |                |   |                        |
| BMI (derived)   | х   |   |                            |                |                                  |                |                |       |                |                |                | Х |                        |
|   |   |   |                            |                |                                  |                |                |       |                |                |                |   |                        |
| Vital signs (BP e , heart rate e , RR) and body temperature | X   | X   |                            | X              |                                  |                |                | x     |                |                |                | X | X                      |

|  | Schedule of Assessments   |   |                             |                           |                                  |  |  |                           |                |  |                |                           |                           |
|--|---|---|-----------------------------|---------------------------|----------------------------------|--|--|---------------------------|----------------|--|----------------|---------------------------|---------------------------|
| Study Period (Duration)  | Screening/
Lifestyle
Stabilization
(Min
4 weeks to
Max
6 weeks) | Screening/
TG
Qualification
(2 Week) | Screening/
TG
Sample  |                           | Double-blind Treatment (8 Weeks) |  |  |                           |                |  |                |                           | Follow-up
(4 Weeks)    |

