| HIV, HCV and HBV Serology l         |   | x   |                            |                                  |   |   |   |   |   |   |   |   |                        |
| FSH if required to determine menopausal status |   | X   |                            |                                  |   |   |   |   |   |   |   |   |                        |
| Serum pregnancy test (WOCBP)                   |   | X   |                            |                                  |   | _ |   |   |   |   |   |   | X                      |
| Urine pregnancy test (WOCBP)                   |   |   | X                          | X                                |   |   |   | X |   |   |   | X |                        |

[figure not shown]
|   | Schedule of Assessments   |   |                            |                                  |   |   |   |   |   |   |   |   |                        |
|---|---|---|----------------------------|----------------------------------|---|---|---|---|---|---|---|---|------------------------|
| Study Period (Duration)   | Screening/
Lifestyle
Stabilization
(Min
4 weeks to
Max
6 weeks) | Screening/
TG
Qualification
(2 Week) | Screening/
TG
Sample | Double-blind Treatment (8 Weeks) |   |   |   |   |   |   |   |   | Follow-up
(4 Weeks) |
| Visits  |   |   |                            |                                  |   |   |   |   |   |   |   |   |                        |
| Study Day b  |   |   |                            |                                  |   |   |   |   |   |   |   |   |                        |
| Jug dispensed for 24-hour urine collection for cortisol and creatinine m |   |   | Х                          |                                  |   |   |   |   |   |   | x |   |                        |
| Archived serum and plasma samples n                                      |   |   |                            | x                                |   |   |   | х |   |   |   | X |                        |
|   |   |   |                            |                                  |   |   |   |   |   |   |   |   |                        |
| Investigational product dosing p   |   |   |                            | X                                | X | X | X | X | X | X | X |   |                        |

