#### 8.2.1. Physical Examinations

- A complete physical examination will include, at a minimum, assessments of the cardiovascular, respiratory, abdominal and a neurological exam. Height (only collected at screening) and weight will also be measured and recorded.
- A symptom directed physical examination will include, at a minimum, assessments of the skin, respiratory, cardiovascular system, and abdomen (liver and spleen).

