## 5 DEFINITIONS

### 5.1 BASELINE DEFINITION

In general, baseline will be defined as the most recent non-missing measurement (scheduled or unscheduled) prior to the administration of the first dose of IP. For numerical measurements that have duplicates or triplicates (for the same visit), the arithmetic mean will be used. Some measurements have special definitions of baseline, which are defined below.

The mean TG value will be used for stratification factor [REDACTED]

Baseline Triglyceride is defined as the average of [REDACTED] and the preceding two lipid-qualifying visits collected in EDC. Fasting status is required for the TG values to be included.

The definition of baseline of other lipid panel labs is the average of last two non-missing screening fasting values and [REDACTED] value (Pre-dose, fasting).

The definition of baseline vital signs is the average of the last two non-missing screening values and [REDACTED]. If there is Case Report Form (CRF) average value on duplicate measurements of BP and/or Pulse on [REDACTED], only the individual values will be included in the baseline derivation.

The baseline definition for MRI for subjects of the main cohort is the [REDACTED] value. The baseline definition for MRI for subjects of the fibrate expansion cohort is the value obtained between [REDACTED]

The baseline definition for safety numeric measurements (except for liver tests) is the average of last two non-missing screening values and [REDACTED]

The baseline definition of PK is the [REDACTED]. The details will be described in a

separate document.

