PK = pharmacokinetics; PT = prothrombin time; RNA = ribonucleic acid; RR = respiratory rate; RLP-C = remnant lipoprotein-cholesterol; SAE = serious adverse event; SoA = Schedule of Assessments; T3 = triiodothyronine; T4 = thyroxine; [REDACTED]; TG = triglyceride; TSH = thyroid-stimulating hormone; V = Visit; VLDL-C = very low-density lipoprotein cholesterol; VLDL-TG = very low-density lipoprotein triglycerides; WBC = white blood cell; WOCBP = women of childbearing potential.

Body posture during TG, BP, heart rate, RR and body temperature measurement needs to be the same (e.g., sitting, semi-erect, or supine) throughout the study with resting for at least 5 min prior to measurement at each study visit.

Fasting blood samples should be taken after at least 12 hours of fasting. (It is recommended that subjects fast no more than 14 hours.) Fasting includes food and all beverages except for non-mineral water.

Hematology: Hemoglobin, hematocrit, RBC count, reticulocyte count, MCV, MCH, MCHC, platelet count, WBC count, total neutrophils, eosinophils, monocytes, basophils, lymphocytes.

Blood chemistry: BUN, creatinine (eGFR using CKD-EPI equation), fasting plasma glucose, calcium, sodium, potassium, chloride, total CO2 (bicarbonate), AST (SGOT), ALT (SGPT), ALP, GGT, total bilirubin, direct (conjugated) bilirubin, indirect (unconjugated) bilirubin, CK, uric acid, albumin, total protein. Coagulation panel: INR, aPTT, PT.

Urinalysis: pH, glucose, protein, blood, ketones, nitrites, leukocyte esterase, urobilinogen, urine bilirubin, microscopy.

a = If [REDACTED] is required, only assessment at that visit is TG measurement.

b = [REDACTED]

c = Symptom-driven physical assessment for applicable reported AEs. Can be conducted on site during a scheduled or unscheduled visit or by a home health provider (HHP) if identified on the delegation log. d = Height at screening [REDACTED] only.

e = Starting from randomization, pre-dose BP and pulse will be measured in duplicate. The first measurement will be initiated before dosing with sitting/semi-erect or supine position and resting for at least 5 minutes prior to measurements. BP and pulse are to be repeated at least 1 minute apart. Additional vital signs measurements may be done if clinically indicated.

f = Coagulation panel will be done at [REDACTED] only.

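### By-visit physical examination tables mix exams of everyone with exams prompted by an adverse event, and skin is tabulated with no required exam of all subjects

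*SAP*

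**What the plan says.** SAP 7.6.4 sets two outputs. The first is by visit: "Physical examination (abdominal, cardiovascular, neurological, respiratory, skin, and general, etc) results will be summarized by visits and by treatment group". The second is a shift table: "Shift tables from baseline to end of the study will be summarized using the category as normal", followed by two abnormal categories split by clinical significance.

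The schedule (Protocol 1.2, repeated in SAP Appendix 1) marks most physical examination entries with footnote c, which SAP Appendix 1 explains: "c = Symptom-driven physical assessment for applicable reported AEs".

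Protocol 8.2.1 defines two kinds of examination. For the full one: "A complete physical examination will include, at a minimum, assessments of the cardiovascular, respiratory, abdominal and a neurological exam". For the other: "A symptom directed physical examination will include, at a minimum, assessments of the skin, respiratory, cardiovascular system, and abdomen (liver and spleen".

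SAP 5.1 gives no baseline rule specific to physical examination, so the general rule applies: "baseline will be defined as the most recent non-missing measurement (scheduled or unscheduled) prior to the administration of the first dose of IP". Protocol section 3 names the incidence and shifts of clinically significant examination findings among the safety endpoints.

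**The concern.** A by-visit table of abnormal findings is read as an incidence over time in each arm. That reading needs the same kind of examination, on the same kind of subject, at each visit shown. Here the examination changes from one for all subjects to one prompted by a reported event, and back again.

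An arm with more reported events would be examined more often and could show more findings for that reason alone. The pattern over time would also shift at end of treatment because the examination rule changes there.

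Skin has the further difficulty that no visit requires a skin examination of everyone. This is a system of interest: Protocol 2.2.3 lists injection site reactions and contact dermatitis among the most common adverse events of the first-in-human study.

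**Working it through.** There is no sample size, power or alpha figure to reproduce. The check is a count of schedule columns and a comparison of examination content.

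**Columns.** The physical examination row in Protocol 1.2 has 13 entries. A plain mark stands in columns 1, 12 and 13. Columns 2 to 11 carry footnote c. So 3 of 13 columns require an examination of all subjects and 13 − 3 = 10 are symptom-driven.

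**Timing.** Visit and day labels are blacked out, so timing is read from position. Columns 1 to 3 sit under screening headings. The row "Investigational product dosing" has 8 marks, in columns 4 to 11. With weekly injections over 8 weeks these are Day 1 to Week 7, which makes column 12 the end-of-treatment visit at Week 8 and column 13 the follow-up visit. Footnote c thus covers 2 screening columns and all 8 dosing columns. After Day 1 there are 7 symptom-driven visits and 2 complete ones.

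**Content.**

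| System in SAP 7.6.4 | Complete exam minimum | Symptom-directed minimum |
|---|---|---|
| Cardiovascular | yes | yes |
| Respiratory | yes | yes |
| Abdominal | yes | yes |
| Neurological | yes | no |
| Skin | no | yes |
| General | not listed | not listed |

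**By-visit table.** For an arm at a footnote-c visit, the abnormal share of the whole arm as recorded equals (share examined) × (abnormal share among those examined).

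- With the whole arm as denominator, the result rises and falls with the share examined, even if the true rates are equal.
- With examined subjects as denominator, it describes mainly subjects with a reported event, not the arm.

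Neither quantity is comparable with columns 12 and 13, where all subjects are due. The SAP does not say which denominator applies. SAP 7.1 shows missing values as a count without a percentage, but does not say whether an examination that was never triggered counts as missing.

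**What sets the trigger.** The adverse event row of the schedule has no mark in columns 3, 5 to 7 and 9 to 11. Where a home provider gives the dose, SAP Appendix 1 (footnote q) relies on spontaneous reports passed to the site. The chance of an examination may therefore also depend on the visit setting. In addition, SAP 6.2 moves an early terminator's end-of-treatment visit to the week in which it fell, so a complete examination can share a cell with symptom-driven ones.

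**Shift table.** SAP 7.6.4 takes shifts only to end of study. The follow-up examination is complete and due for all subjects, so the endpoint is unselected for the four systems in the complete minimum. For skin it is not.

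**The case against.** The strongest reply is that little safety information is lost. An abnormal finding judged clinically significant, and not attributed to the underlying disease, is itself an adverse event under Protocol 10.3.1 and reaches the treatment-emergent tables for the whole Safety Analysis Set. A footnote-c examination exists because an event was already reported. The missing-count row in SAP 7.1 could reveal sparse examination. The table shells and the case report form are not available and may settle the denominator. The stated content is only a minimum, and SAP 7.6.4 also lists a general category found in neither minimum list, so sites may well record skin at complete examinations. All of this stands, and it keeps the point small. It does not make the by-visit rows comparable, and it leaves skin to site practice.

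Three stronger readings are tempting, and the documents do not support them.

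- A reader might infer that all the shift tables follow who was examined. For cardiovascular, respiratory, abdominal and neurological findings, the end-of-study examination is due for everyone.
- A reader might infer that the baseline rule biases the arms, because a symptom-driven examination before dosing can replace the complete screening one. Such an examination precedes treatment, so the assigned arm cannot influence it. Fixing baseline at the first screening examination would be worse: screening runs about 6 to 9 weeks, and a finding that arose in that time and persisted would be counted as an on-treatment shift.
- A reader might want a fold difference between arms. The documents give neither the frequency of triggered examinations nor the share that are abnormal, so any such figure would be assumption alone.

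**Conclusion.** The point holds for two outputs: the by-visit summary in the 10 footnote-c columns, and skin results at every visit, including the skin shift. As written, the former reflect selection by reported events, and the latter have no required examination of all subjects.

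The size can be stated only as coverage: 3 of 13 columns with an examination of everyone for four systems, and none for skin. No bias in percentage points can be derived. The conclusion assumes that column position gives the timing of the blacked-out visits, and that the unseen table shells add no restriction.

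The effect is confined to descriptive safety tables; no efficacy analysis, power or alpha changes. This is a cheap improvement.

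**What to change.** In SAP 7.6.4, limit the by-visit summary to the complete-examination visits (first screening, end of treatment, follow-up), with the number of subjects examined as denominator. Put symptom-driven examinations in a listing linked to the adverse event that prompted each. State where an early terminator's complete examination is shown, since SAP 6.2 moves it to an earlier week.

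Reconcile skin between SAP 7.6.4 and Protocol 8.2.1. Either add skin to the minimum content of the complete examination or, if the data are already collected and skin was not examined in all subjects, drop skin from the shift table and report it through adverse events. Keep the last pre-dose baseline rule.

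The cost is a few sentences of SAP text and a shorter table. Adding skin needs no extra visit, but does need a protocol change. The downside is that symptom-driven findings at the footnote-c visits appear only in a listing and through adverse events.
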